5.3 Exclusion Criteria

Subjects who meet **any** of the following criteria are not eligible for enrollment as study participants:

- Known allergy or hypersensitivity to sirolimus
- Inability or refusal to provide informed consent

- Advanced respiratory support (high flow oxygen \geq 15 L/min, CPAP, non-invasive or invasive mechanical ventilation). CPAP use for treatment of obstructive sleep apnea is not an exclusionary criterion.
- Active enrollment in other interventional clinical drug trials. Co-enrollment in observational studies and biorepositories is allowed.
- On chronic immunosuppression for other medical conditions such as rheumatological disorders, inflammatory bowel disease, or in patients with organ transplants. A list of prohibited medications is provided in Section 12.3.4.
- Pregnant women
- Breast feeding
- Any clinically significant medical disease which in the opinion of the investigator precludes the patient from enrolling in the trial, including (but not limited to):
 - History of liver cirrhosis
 - End stage renal disease or need for renal replacement therapy
 - Decompensated heart failure
 - Known active tuberculosis or history of incompletely treated tuberculosis
 - Uncontrolled systemic bacterial or fungal infections
 - Active viral infection other than COVID-19
 - Lymphoma or other systemic malignancies, either current or treated within the past 2 years. Localized non-melanoma skin cancer is not an exclusion.

5.4 Recruitment

After IRB and DSMB approval has been obtained, the screening and identification for subjects will be performed as described in Section 5.1. Interested individuals will be provided with detailed study information and the informed consent form (ICF). After they have had a chance to review the study procedures and the ICF, and after ensuring that all questions are answered, patients can be enrolled into the study. Details of the informed consent process are provided in Section 6.3.

5.5 Study Drug Treatment

Patients who meet eligibility criteria, provide informed consent and are enrolled in the study will be randomized to receive sirolimus or placebo in a double-blind manner and a 2:1 randomization scheme in favor of sirolimus. The sirolimus dose for the study will be 6mg daily on day 1 followed by 2mg daily for a maximum treatment duration of 14 days, or until hospital discharge, whatever happens first. The study drug will be provided by the drug manufacturer, Pfizer, encapsulated and dispensed by the University of Cincinnati's Investigational Drug Services (IDS) Pharmacy, and given to the patients by their bedside nurse. Patients will be reminded about the side effects of sirolimus. Every attempt will be made to give the medication at the same time every day. Chart reviews will be conducted on a daily basis to determine changes in clinical status, concomitant medications and laboratory parameters. Study specific biomarkers will be measured at baseline and then at days 3, 7 and 14. Section 6.2 provides a detailed description of the study specific schedule of events. Patients will be instructed to

contact the study staff should they experience any side effects. Study drug may be held or reduced in the event of unacceptable side effects.

5.6 Treatment Regimen

Patients will be randomized to either a 6mg oral loading dose of sirolimus followed by 2mg daily for a maximum treatment duration of 14 days, or matching placebo. We have chosen this dosing strategy to mirror the typical regimen in patients who start sirolimus following a kidney transplant, in order to ensure rapid therapeutic mTOR inhibition in these patients. The 2mg daily dose is also consistent with the Chinese randomized clinical trial that showed a clinically useful beneficial effect of sirolimus in critically patients with H1N1 influenza.²⁴

6. Study Procedures and Timelines

6.1 Study and Timeline Overview

Patients will be identified by the medical and research staff at the University of Cincinnati Medical Center and the facilities of the affiliated health systems UC Health, LLC and University of Cincinnati Physicians Company, LLC. Recruitment will take place until 30 evaluable patients have been enrolled, or the incidence of new cases does not permit further enrollment. Patients who meet eligibility criteria, provide informed consent and are enrolled in the study will receive instructions regarding study drug dosage, route and administration. The study drug will be given each morning along with other inpatient medications at roughly the same time every day. Patients will be on the study drug for a maximum duration of 14 days, or until hospital discharge, whatever happens first. In case a patient progresses to require advanced respiratory support, the study drug can continue as scheduled at the discretion of the treating clinician(s). If deemed clinically necessary on a case-by-case basis, in these scenarios the patient may need to be withdrawn ± unblinded.

All study procedures will take place after obtaining informed consent. Details of the informed consent process are provided in Section 6.3. Prior to starting study drug, baseline demographic and clinical variables will be collected along with vital signs, amount of supplemental oxygen required, laboratory biomarkers such as absolute lymphocyte count, ferritin, LDH, and d-dimer, renal and liver function tests, concomitant medications, past medical history, and results of the chest imaging. After study initiation, chart reviews will be conducted on a daily basis to assess vital signs, changes to concomitant medications, lab values, and oxygenation indices. Study-specific biomarkers: absolute lymphocyte count, serum ferritin, d-dimer and LDH will be measured at Day 3, 7 and 14 following study initiation, unless already checked clinically in the 24 hours prior to the testing time.

6.2 Schedule of Events

Event	Screening ¹	D1	D2	D3	D4	D5	D6	D7	D8	D9	D10	D11	D12	D13	D14 ⁶	F/u ⁷
Informed consent	X															
Demographics	X															
Medical history	X															
Determine study eligibility	X															
Con meds	X	X	X	X	X	X	X	X	X	X	X	X	X	X	X	
Review AEs			X				X								X	
Heart rate/pulse ²	X	X	X	X	X	X	X	X	X	X	X	X	X	X	X	
MAP ²	X	X	X	X	X	X	X	X	X	X	X	X	X	X	X	
Highest daily temperature (F)	X	X	X	X	X	X	X	X	X	X	X	X	X	X	X	
Oxygen saturation ²	X	X	X	X	X	X	X	X	X	X	X	X	X	X	X	
FiO ₂ (%) ^{2, 3}	X	X	X	X	X	X	X	X	X	X	X	X	X	X	X	
Pregnancy test ⁴	X															
LDH ⁵	X			X				X							X	
Ferritin ⁵	X			X				X							X	
D-dimer ⁵	X			X				X							X	
Absolute lymphocytes ⁵	X			X				X							X	
CBC (WBCs, Hb, Platelets) ⁵	X			X				X							X	
Serum creatinine ⁵	X			X				X							X	
AST, ALT ⁵	X			X				X							X	
Advanced resp. support (Y/N)	X	X	X	X	X	X	X	X	X	X	X	X	X	X	X	
Vital status	X	X	X	X	X	X	X	X	X	X	X	X	X	X	X	

¹ Screening visit can be the initial visit if a patient meets all inclusion/exclusion criteria

² Mean recorded value for the 24-hour duration of that day

³ FiO₂ (%) will be recorded if directly available from chart review such as in patients on ultra-high flow devices (vapotherm, optiflow etc.) or in patients on advanced respiratory support. For all other patients, FiO₂ (%) will be calculated based on the following conversion:

Supplemental O ₂ (l/min)	0	1	2	3	4	5	6	7	8	9	10	11	12	13	14
FiO ₂ (%)	21	24	27	30	33	36	39	42	45	48	51	54	57	60	63

⁴ Only required for women of childbearing potential, if not already obtained clinically

⁵ No need to recheck if already drawn clinically in the 24 hours prior to the study-specified time. If not checked clinically, these can be measured as research tests. If COVID-19 biorepository sample obtained on the day of these tests, they can be postponed to the next day.

⁶ In case a patient is discharged from the hospital before the 14-day period, their last hospital day will be treated similar to Day 14 with regards to study assessments

⁷ Long term outcomes following the 14-day study period will be assessed by chart reviews

Abbreviations: AE = adverse event, ALT = Alanine aminotransferase, AST = Aspartate aminotransferase, CBC = complete blood count, F = degrees Fahrenheit, FiO₂ = Fraction of inspired oxygen, Hb = Hemoglobin, LDH = Lactate dehydrogenase, MAP = Mean arterial pressure, WBCs = White blood cells

6.3 Study Visits

Screening/Initial Visit

All study procedures will begin only after the subject has completed the informed consent process.

Informed consent process for this study: Potential study patients will be contacted by the study staff to determine interest in study participation. Interested individuals will be provided with detailed study information and a copy of the ICF. Patients will be given ample time to read and discuss the ICF with the study staff. The study staff will then answer any remaining questions asked by the patients. The patients will be offered the option of signing the consent form. Those who agree to participate will undergo the remainder of study procedures. In order to prevent transmission of COVID-19 from ICFs that have been in physical contact with the patients (e.g. during the act of obtaining signatures), we will obtain consent by following either the quarantine consent process or the telephone consent process, as detailed below.

Quarantine Consent

- The subject (or their legally authorized representative (LAR)) will be provided with a copy of the ICF to keep at the bedside during the quarantine period.
- The informed consent discussion will be presented to the subject (or their LAR) by an authorized study representative (investigator/coordinator) who is sufficiently knowledgeable about the research to properly interpret and correctly answer questions.
- A witness who is not a member of the study team will be present for the informed consent discussion.
- We will identify all participants and their role in the study (e.g. study staff, patient, next of kin, LAR, impartial witness etc.).
- We will review the ICF in a comprehensive manner with the patient (or their LAR), solicit and answer all questions.
- The subject (or their LAR), study team member obtaining informed consent, and the witness will sign the subject's (or their LAR's) copy of the ICF. The subject will keep the original ICF for their records.
- Immediately after the informed consent discussion, the investigator and witness will document their signatures on a separate ICF outside of isolation/quarantined areas. We will document "Quarantine consent obtained" in the subject's (or their LAR's) signature line.

Telephone Consent

The following stepwise process will be followed in order to obtain telephone consent from interested subjects prior to study enrollment.

- A copy of the ICF will be provided to the subject (or their LAR) to review over the phone.

- The informed consent discussion will be presented to the subject (or their LAR) by an authorized study representative (investigator/coordinator) who is sufficiently knowledgeable about the research to properly interpret and correctly answer questions.
- A witness who is not a member of the study team will be present for the informed consent discussion with the investigator/study coordinator.
- We will begin the call by identifying all participants on the call and their role in the study (e.g. study staff, patient, next of kin, LAR, impartial witness etc.)
- Next, we will review the ICF in a comprehensive manner with the patient (or their LAR), solicit and answer all questions.
- We will obtain verbal confirmation from the witness that the subject's questions have been answered.
- Obtain verbal confirmation from the subject (or their LAR) regarding their agreement to participate in the study, and that they have signed the ICF in their possession while the witness is still on the telephone.
- Obtain verbal confirmation from the study staff member that the subject has agreed to participate in the study and sign the ICF while the witness is still on the telephone.
- The investigator and witness will sign the ICF and document "telephone consent obtained" in the subject's (or their LAR's) signature line.

Script for telephone consent

1. Hello, my name is _____ . I am calling from the University of Cincinnati regarding a research study for COVID-19. We are conducting a study to assess if an already approved medication called sirolimus can help patients hospitalized with COVID-19. I'd like to ask your permission to tell you about the study.

If the patient and/or LAR is agreeable, proceed with the following: I would like to provide you with a copy of the informed consent form for you to keep and arrange a time that I can call you back to answer any questions you may have. It is important that you have time to read the consent form and have it with you when we talk about the study.

2. Hello, this is _____ calling back about the COVID-19 study at the University of Cincinnati. Is this a good time? Also present on this phone call is _____, who will act as a witness to our conversation and be present throughout the phone call. Do we have your permission to proceed?

If the patient agrees, we will confirm that the patient has access to a copy of the ICF with them and proceed with the steps outlined above. Prior to obtaining signatures, we will explicitly solicit any questions from the subject and ensure that all questions have been answered to their satisfaction.

After obtaining informed consent, we will review the inclusion/exclusion criteria to determine study eligibility. For patients who provide informed consent and meet all eligibility criteria, the screening visit can be their initial study visit. We anticipate that in most patients the

screening visit will be the initial study visit, and the following additional steps will be completed during the visit:

- Review medical history
- Record current medications
- Record vital signs: heart rate, blood pressure, temperature as specified in Section 6.2
- Record baseline oxygenation indices: oxygen saturation and FiO_2 as specified in Section 6.2
- For women of childbearing potential, obtain a urine pregnancy test, if not already obtained during the hospitalization
- If not already obtained clinically in the previous 24 hours, then obtain measurements for study specific biomarkers: LDH, ferritin, d-dimer, and absolute lymphocyte count
- If not already obtained clinically in the previous 24 hours, then obtain other laboratory parameters: CBC (total WBCs, Hb, Platelets), serum creatinine, AST, and ALT

Subsequent visits

Subjects' medical chart will be reviewed on a daily basis after study enrollment. The following parameters will be obtained on a daily basis from chart review:

- Vital signs: heart rate, blood pressure, temperature as specified in Section 6.2
- Oxygenation indices: oxygen saturation and FiO_2 as specified in Section 6.2
- Concomitant medications
- Advanced respiratory support use status
- Vital status

In addition, the following activities will be performed on days 3, 7 and 14 of the study

- If not already obtained clinically in the previous 24 hours, then obtain measurements for study specific biomarkers: LDH, ferritin, d-dimer, and absolute lymphocyte count. If COVID-19 biorepository sample obtained on the day of these tests, they can be postponed to the next day.
- If not already obtained clinically in the previous 24 hours, then obtain other laboratory parameters: CBC (total WBCs, Hb, Platelets), serum creatinine, AST, and ALT
- Query the patient with regards to any adverse effects from the study medication. This can be done remotely via telephone interview rather than in-person visit in order to minimize study staff exposure as well as preserve PPE

In case a subject is discharged from the hospital before Day 14, every effort will be made to complete the day 14 activities on the day of hospital discharge. In case the duration of hospitalization extends beyond the study duration of 14 days, we will periodically monitor the electronic medical record and record key variables such as the need for advanced respiratory support, duration of hospitalization, duration of ICU status, time spent on mechanical ventilation, and vital status.

6.4 Enrollment

Enrollment in the study will continue until the enrollment target of 30 patients is reached. This research study will be explained in lay terms to each potential research participant. The potential participant will sign an ICF before undergoing any screening study procedures. Participants who are deemed eligible for the study (see Section 6.3) will be enrolled and assigned a unique participant ID number.

6.5 Consent for future contact

During the consent process, patients will have the option to provide permission for future contact. This permission allows for patient contact information, including their full name, address and telephone number, to be retained. The permission for future contact allows for possible patient re-contact regarding future IRB-approved studies. If the patient denies permission, no future contact will be made.

6.6 Consent for continuing data review of medical records

During the consent process, patients will have the option to provide permission for future data review of their medical records. This permission allows for study staff to contact the patient (or the patient's caregiver(s)) to obtain medical records and other information for a period of up to two years after the patient has withdrawn from or completed the study. The purpose of this data review is to capture information including but not limited to clinical, radiographic, pathologic, laboratory and pulmonary function data, after the patient has exited the study. The rationale for future data review is that there may be long term effects of COVID-19 or the study drug, that are unknown to the investigators at this time.

7. Stopping rules

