7.2 Criteria for terminating the study

Up to 30 patients will be enrolled in this study. The maximum duration of patient participation is 14 days. In the event of any death or Grade IV Serious adverse event (SAE) that is unexpected and attributable to the study agent, enrollment will be suspended, pending Data Safety Monitoring Board (DSMB) review.

8. Study variables and measuring methods

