8.5 Other study parameters

Daily chart reviews will be performed to record other variables of interest:

Need for advanced respiratory support: Recorded as Yes/No and type, whether high flow oxygen \geq 15 liters/minute, CPAP, non-invasive, or invasive mechanical ventilation. If a patient receives more than one form of advanced respiratory support in the same day, (e.g. started on non-invasive and worsens to require invasive ventilation, or extubated from invasive to non-invasive ventilation), we will designate the most advanced form of ventilation (in the above scenarios – mechanical ventilation) for that day. The ranking order for the above modes of respiratory support are (from most advanced to least advanced means): 1. Mechanical ventilation, 2. Non-invasive ventilation (e.g. bilevel), 3. CPAP, 4. High flow supplemental oxygen \geq 15 L/minute. Of note, the use of CPAP employed to treat pre-existing obstructive sleep apnea will not count as advanced respiratory support.

Duration of advanced respiratory support: For patients who progress to require advanced respiratory support, the type(s) of support and the time spent on the support (individual modes as well as cumulative, days) will be recorded.

Vital status: The vital status (alive/deceased) will be recorded at study termination as well as at the time of hospital discharge (in case that happens after the 14-day study period). For non-survivors, the time from study initiation to death will also be recorded.

Duration of hospital stay (days): will be recorded starting from the day of admission to the day of hospital discharge. This parameter will only be used for analysis in patients who survive the hospital stay.

9. Risks

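### Patients withdrawn before hospital discharge have no assured chart follow-up to discharge or death, so survival to discharge, length of stay and some later progressions can be missed

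*Combined protocol and SAP*

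**What the plan says.** Three places commit to looking past Day 14. Section 6.3: "In case the duration of hospitalization extends beyond the study duration of 14 days, we will periodically monitor the electronic medical record", with respiratory support, length of stay and vital status among the items. Section 8.5 says that vital status "will be recorded at study termination as well as at the time of hospital discharge", and expressly covers a discharge later than Day 14. Footnote 7 of the Schedule of Events: "Long term outcomes following the 14-day study period will be assessed by chart reviews". None of the three attaches a consent condition.

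Two other places use narrower wording. Section 7.2: "The maximum duration of patient participation is 14 days". Section 6.6 says that "patients will have the option to provide permission for future data review of their medical records"; the permission runs "for a period of up to two years after the patient has withdrawn from or completed the study", and the section explains why: "The rationale for future data review is that there may be long term effects of COVID-19 or the study drug".

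For withdrawn patients the relevant rules are these:

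- Section 7.1(d) allows withdrawal on ICU transfer or need for advanced respiratory support, on the treating clinician's judgement. Section 7.1(e) allows it on the investigator's opinion.
- Section 8.3 moves the Day 14 laboratory assessments to the day of withdrawal.
- Section 13.1.2 declares an intent-to-treat approach and says that data acquired before termination enter the primary analysis unless consent is withdrawn.
- Section 13.1.4 undertakes to try to obtain endpoint evaluations after withdrawal, and then times them at termination.
- Section 13.2 follows patients taken off study drug for adverse events, for safety, until discharge, resolution or stabilization, or a decision by the principal investigator.

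**The concern.** Survival to hospital discharge is a key secondary endpoint (section 4.3). Duration of stay, duration of advanced support and time to death are also listed there. Each needs the chart up to discharge or death. The primary analysis is by intent to treat, which needs progression status for every randomized patient whether or not study drug continued.

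Withdrawal under 7.1(d) is triggered by deterioration, so it is linked to outcome. If observation ends on that day, the patient is recorded as alive when last seen, and a later death in the same hospital stay has no assured route into the data. A patient withdrawn before reaching the primary endpoint, for example on ICU transfer without advanced support or under 7.1(e), could progress afterwards unrecorded. Either loss weakens a comparison that rests on 10 placebo and 20 sirolimus patients.

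**Working it through.** **Step 1. Which patients have an assured route to discharge status?**

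- *Discharged by Day 14 without withdrawal:* daily vital status and respiratory support under the Schedule of Events. Complete.
- *In hospital after Day 14, not withdrawn:* 6.3, 8.5 and footnote 7. Complete as written.
- *Withdrawn for an adverse event (including 7.1(c)):* 13.2 gives safety follow-up, but it may end before discharge. Partial.
- *Withdrawn under 7.1(d) or (e) for another reason:* final evaluations at withdrawal (8.3, 13.1.4), nothing under 13.2, and later review named as optional in 6.6. Not assured.
- *Consent withdrawn (7.1(a)):* loss may be unavoidable.

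The discharge entry in 8.5 does not clearly rescue the fourth group. Its parenthesis concerns discharge after Day 14. A patient withdrawn on Day 5 who dies in hospital on Day 10 falls outside it. Adverse-event collection stops at the end of treatment (14.4.1), so safety reporting is not a dependable substitute.

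**Step 2. The plan's own precision.** Inputs from section 15: 30 patients at 2:1, so 10 placebo and 20 sirolimus; rates 0.50 and 0.25; 80% interval, z = 1.2816.

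SE = √(0.50×0.50/10 + 0.25×0.75/20) = √(0.025 + 0.009375) = 0.1854.

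Interval: 0.25 ± 1.2816×0.1854 = 0.25 ± 0.238, or 0.012 to 0.488. It excludes zero by 0.012, less than the weight of one patient in either arm.

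**Step 3. Weight of one patient.** Placebo 1/10 = 0.10; sirolimus 1/20 = 0.05. With m_P and m_S unknown outcomes, the best-case to worst-case range of the difference widens by m_P/10 + m_S/20. For assumed counts:

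- 1 sirolimus and 1 placebo: 0.15
- 2 and 1: 0.20
- 4 and 2: 0.40

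**Step 4. Primary endpoint, one progression missed and counted as none (illustration).**

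- Placebo 4/10 against 5/20: difference 0.15, SE = √(0.024 + 0.009375) = 0.1827, interval −0.084 to 0.384.
- Placebo 5/10 against 4/20: difference 0.30, SE = √(0.025 + 0.008) = 0.1817, interval 0.067 to 0.533.

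The direction depends on the arm in which the event is missed.

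**Step 5. Survival to discharge (assumed deaths; 80% interval borrowed from the primary analysis).**

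- All known, 3/10 against 2/20: 0.20 (−0.005 to 0.405).
- One late placebo death missing, 2/9 against 2/20: 0.12 (−0.075 to 0.320).
- The same death scored as alive, 2/10 against 2/20: 0.10 (−0.083 to 0.283).

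**The case against.** A reader might infer something broader: that any patient still in hospital on Day 15 has completed the study under 7.2, so that the chart may be read only with the 6.6 permission and late deaths are at risk in all long-stay patients. The documents do not support this. Sections 6.3 and 8.5 and footnote 7 each name the 14-day limit and still require review beyond it, and no section makes that review depend on the option. Section 6.6 provides for contacting patients or caregivers to obtain records for up to two years, because of long-term effects, which reads as an addition. What remains for this group is loose wording to be aligned.

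For withdrawn patients, the best defence is the 13.1.4 undertaking to seek endpoint evaluations. It shows the right intention, but its timing at termination cannot supply survival to a later discharge. Section 13.1.2 does not forbid using later data; it is silent on them.

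Three further points stand. The 6.6 choice is made at consent, before treatment and outcome, so nothing suggests that refusal differs by arm. The SAP sets no test or decision rule for survival to discharge. The consent pages are not available for review, so the main consent may already cover chart review to discharge.

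**Conclusion.** The point holds for patients withdrawn before discharge, chiefly under 7.1(d) or (e) for reasons other than an adverse event. For them the stated rules can end observation at withdrawal, despite the intent-to-treat declaration. Survival to discharge and length of stay are the outcomes most exposed. The primary endpoint is affected only in patients withdrawn before an event; anyone withdrawn because of advanced support has already met it.

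Each unknown outcome is worth 10 points in the placebo arm or 5 in the sirolimus arm, assuming the planned 10 and 20 patients. How many would be lost cannot be derived, because the documents give no withdrawal, refusal or late-death rates; the counts in steps 3 to 5 are illustrations. Lost deaths are a possible result of the wording, and nowhere does the plan prescribe scoring such patients as alive. For patients still on study after Day 14, only the wording of 6.6 and 7.2 needs aligning.

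**What to change.** - In 7.1, 13.1.2 and 13.1.4, state that chart review for respiratory support, vital status and length of stay continues to hospital discharge or death for every randomized patient, including those withdrawn from study drug or procedures, unless the patient specifically withdraws consent to data collection. State that these data enter the analysis.
- In 6.6, limit the optional permission to data after discharge.
- In 7.2, separate the 14-day treatment period from outcome follow-up to discharge or death.
- Check that the main consent covers this review, and add it only if it does not.

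None of this changes when a patient may be withdrawn or unblinded. The cost is one amendment and possibly a slightly broader main consent. It needs no extra visits or tests, only the existing chart review carried on for withdrawn patients.
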